4 OBJECTIVES AND ENDPOINTS

Table 4-1: Objectives and Endpoints

Objective	Endpoint
Primary	

 To demonstrate the superiority in efficacy of abatacept compared with adalimumab, both on background MTX, in achieving clinical response (ACR50) at Week 24, in early, seropositive (RF+ and ACPA+) RA patients with the SE HLA Class II risk alleles (ie, SE+). 	
 Proportion of SE+ participants meeting ACR50 response at Week 24
Key Secondary	

 To compare the efficacy of abatacept with adalimumab, both on background MTX, in achieving clinical remission criteria (DAS28-CRP remission) at Week 24 in early, seropositive RA patients with the SE HLA Class II risk alleles (ie, SE+). 	
 Proportion of SE+ participants achieving DAS28-CRP remission (DAS28-CRP < 2.6) at Week 24

 To compare the efficacy of abatacept with adalimumab, both on background MTX, in achieving clinical response (ACR50) at Week 24 in the whole study population of early, seropositive RA patients. 	
 Proportion of whole study population participants meeting ACR50 response at Week 24

Table 4-1: Objectives and Endpoints

Objective	Endpoint

 To compare the efficacy of abatacept with adalimumab, both on background MTX, in achieving clinical remission criteria (CDAI remission) at Week 24 in early, seropositive RA patients with the SE HLA Class II risk alleles (ie, SE+). 	
 Proportion of SE+ participants achieving CDAI remission (CDAI ≤ 2.8) at Week 24

 To compare the efficacy of abatacept with adalimumab, both on background MTX, in achieving improvement in pain at Week 24 in early, seropositive RA patients with the SE HLA Class II risk alleles (ie, SE+). 	
 Mean change from baseline in SE+ participant-reported pain (VAS) at Week 24
Other Secondary	

 To determine the efficacy over time by treatment in early, seropositive RA patients (SE+ subset and whole population). 	
 Proportion of SE+ subset and whole population achieving ACR20/50/70 responses, DAS remission, CDAI remission, SDAI remission over the SBTP and OLTP; mean changes from baseline in DAS28-CRP, CDAI, SDAI over the SBTP and OLTP; mean changes from baseline in the 7 ACR core components over the SBTP and OLTP

 To determine the improvement in health-related quality of life over time by treatment in early, seropositive RA patients (SE+ subset and whole population). 	
 Mean change from baseline in SF-36 in SE+ subset and whole population at Week 24 and Week 104 (4 physical and 4 mental subscales and the physical component and mental component summary)
Exploratory	

 To assess improvement in work and productivity over time. 	
 Mean change from baseline in WPAI-RA score at Week 24 and Week 104

 To assess improvement of fatigue over time. 	
 Mean change from baseline in FACIT-F score at Week 24 and Week 104

 To assess improvement in duration of morning stiffness over time. 	
 Mean change from baseline in duration of morning stiffness at Week 24 and Week 104

 To assess/explore biomarkers, including: 
 Serum proteins Genetic risk alleles 	
 autoantibodies Target gene (eg, HLA-DRB1,)

Abbreviations: +, positive; ACPA, anti-citrullinated protein antibodies; ACR20/50/70, 20%/50%/70% improvement in American College of Rheumatology criteria; CDAI, Clinical Disease Activity Index; DAS, disease activity score; DAS28-CRP, Disease Activity Score 28-joint count calculated using C-reactive protein; FACIT-F, Functional Assessment of Chronic Illness Therapy - Fatigue; HLA-DRB1, human leukocyte antigen Class II histocompatibility antigen; MTX, methotrexate; OLTP, Open-label Treatment Period; RA, rheumatoid arthritis; RF, rheumatoid factor; SBTP, Single-blind Treatment Period; SDAI, Simple Disease Activity Index; SE, shared epitope; SE+, shared epitope-positive; SF-36, 36-item Short Form Survey; VAS, visual analog scale; WPAI-RA, Work Productivity and Activity Impairment Questionnaire - Rheumatoid Arthritis.

5 STUDY DESIGN

5.1 Overall Design

This is a randomized, single-blind, multicenter, global Phase 3 study. The head-to-head study is designed to evaluate the superiority in efficacy of abatacept compared with adalimumab in a population of RA patients who have early disease and are MTX-IR, seropositive (RF+ and ACPA+), and expressing SE HLA Class II risk alleles (ie, SE+).

[figure not shown]
Eligible participants will include adults (≥ 18 years old) who have early RA, defined as symptoms of RA (pain, stiffness, or joint swelling) for no more than 12 months prior to screening, and satisfy the ACR/EULAR 2010 criteria for the classification of RA at some point during the 12-month period prior to signing the informed consent form (ICF). Participants who had a single isolated episode of palindromic symptoms that occurred less than 2 years prior to enrollment are still eligible. Participants must have a second-generation anti-CCP-2 test result that is greater than $3 \times$ ULN and be RF+ at screening according to central laboratory testing. The anti-CCP-2 test is commonly used in the clinic to measure ACPA, and the $3 \times$ ULN cutoff in the anti-CCP-2 central laboratory test ensures a stable positive ACPA profile. Participants must have a DAS28-CRP of at least 3.2 at screening and have at least 3 tender and at least 3 swollen joints (excluding distal interphalangeals) at screening and at randomization.

Eligible participants must have been treated with MTX for at least 12 weeks prior to randomization with a stable dose of oral or parenteral MTX for at least 4 weeks prior to randomization (ie, MTX-IR). The stable dose of oral or parenteral MTX should be the maximum tolerated oral or parenteral dose (expected doses from 15 mg to 25 mg per week; see [Section 7.1.3](#)). Participants may enroll with MTX doses < 15 mg/week but ≥ 7.5 mg/week if intolerance to higher doses has been documented and the dose of oral or parenteral MTX is stable for 4 weeks prior to randomization. Participants in Japan may also enroll at doses between 7.5 and 15 mg per week at the discretion of the investigator. Participants must be naive to prior therapy with other DMARDs, except brief exposure to either sulfasalazine or hydroxychloroquine. See [Section 6](#) (Study Population, Inclusion/Exclusion Criteria) for additional details.

The study is divided into 4 periods: Screening Period, Single-blind Treatment Period (SBTP) from Day 1 to Week 24, Open-label Treatment Period (OLTP) from Week 24 to Week 104, and Post-treatment Follow-up Period (PTFUP).

The study design schematic is presented in [Figure 5.1-1](#).

Figure 5.1-1: Study Design Schematic

Abbreviations: ACPA+, anti-citrullinated protein antibody-positive; D, Day; MTX, methotrexate; MTX-IR, methotrexate inadequate responders; OLTP, Open-label Treatment Period; R, randomize; RA, rheumatoid arthritis; RF+, rheumatoid factor-positive; SBTP, Single-blind Treatment Period; SC, subcutaneous.

^a In reference to Day 729 for participants who complete the OLTP or the day of last study treatment for participants who discontinue study treatment during the SBTP or OLTP.

5.1.1 Screening Period

Eligibility will be based on specified inclusion and exclusion criteria, medical history, disease activity, and safety assessments. Randomization must occur within 28 days of signing the ICF. Participants that experience delays may extend the screening period to 42 days (see [Section 6.4.1.2](#)). Rescreening is allowed (see [Section 6.4.1.3](#)).

5.1.2 Treatment Period

5.1.2.1 Single-blind Treatment Period: Day 1 - Week 24

On Day 1, participants will begin the SBTP and be randomized according to a computer-generated fixed-block randomization schedule. The site must complete the Tender (68)/Swollen (66) Joint Count to verify the final inclusion criteria (at least 3 tender and at least 3 swollen joints, excluding distal interphalangeals) prior to contacting Interactive Response Technology (IRT) for randomization. The site must also have the results of the genotyping for the SE from the central lab prior to randomization because participants will be stratified by SE status (positive or negative). Participants will be randomized to 1 of 2 parallel treatment arms in a 1:1 ratio:

- 1) Abatacept SC (125 mg) weekly with background stable MTX therapy
- 2) Adalimumab SC (40 mg) once every 2 weeks with background stable MTX therapy

Abatacept and adalimumab administration: On Day 1, participants and/or personal caregivers will be trained in self-administration of SC injections using prefilled syringes.

Methotrexate: Participants must have been treated with MTX for at least 12 weeks prior to randomization with a stable dose of oral or parenteral MTX for at least 4 weeks prior to randomization. The stable dose of oral or parenteral MTX should be the maximum tolerated dose (minimum of 15 mg and maximum of 25 mg per week). A dose of MTX < 15 mg/week but ≥ 7.5 mg/week is permitted if intolerance to higher doses has been recorded in the source documents and the dose of oral or parenteral MTX is stable for 4 weeks prior to randomization. Participants in Japan may also enroll at doses between 7.5 and 15 mg per week at the discretion of the investigator. For complete details of MTX use, see [Section 7.1.3](#).

5.1.2.2 Open-label Treatment Period: Week 24 - Week 104

At Week 24, all participants ongoing in the OLTP will receive abatacept 125 mg SC weekly for the duration of the treatment period:

- 1) Participants receiving abatacept SC (125 mg) weekly will continue to receive abatacept.
- 2) Participants receiving adalimumab SC (40 mg) will switch to abatacept SC (125 mg) weekly at Week 24.
- 3) Participants will continue to be treated with oral or parenteral MTX as described above.
- 4) Participants not wishing to continue on open-label abatacept have the option of discontinuing treatment at the end of the SBTP and continuing to the PTFUP.

5.1.3 Post-treatment Follow-up Period

There will be a PTFUP for safety assessments. This period will be required only for some participants based on how they will be treated after study completion or Early Termination (ET). Participants who complete the treatment periods (ie, OLTP) or discontinue prior to completing the OLTP AND are not treated with post-study abatacept, regardless of the source, will need to complete the PTFUP. This will consist of 2 follow-up visits on Day 85 and Day 169 post cessation of investigational product (IP; see [Table 2-4](#)). The PTFUP will begin on Day 729 for participants who complete the OLTP. The PTFUP will begin on the day of last study treatment for participants who discontinue study treatment during the SBTP or OLTP. Participants who complete the OLTP or discontinue at any time prior to completing the OLTP AND are treated with post-study abatacept, regardless of the source, will not need to complete the PTFUP.

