Procedure	Week 12 FU V1 (± 10 days) ^a	Week 24 FU V2 (± 10 days) ^a	Notes
	Day 85	Day 169	
Safety Assessments			
Vital Signs	X	X	Body temperature, seated blood pressure, and heart rate.
Adverse Events Assessment	X	X	
Concomitant Medication Report	X	X	
Laboratory Assessments			
Urine Pregnancy Test	X	X	WOCBP only; serum test if needed (see Section 9.4.7). Performed locally.

Abbreviations: FU, Follow-up; OLTP, Open-label Treatment Period; PTFUP, Post-treatment Follow-up Period; SBTP, Single-blind Treatment Period; V, Visit; WOCBP, women of childbearing potential.

^a Visits only apply to participants who complete the study at Day 729 or discontinue study treatment during the SBTP or OLTP AND are not treated with abatacept as a post-study drug. The first day of the PTFUP is Day 729 for participants who complete the OLTP or the day of last study treatment for participants who discontinue study treatment during the SBTP or OLTP. Participants who complete the OLTP or discontinue at any time prior to completing the OLTP AND are treated with post-study abatacept, regardless of the source, will not need to complete the PTFUP. The follow-up visit should ideally be an in-person visit. If this is not possible, a telephone follow-up visit will be performed to confirm the results of the urine pregnancy test as well as adverse event and concomitant medication review. Vital signs will not be collected as part of a telephone follow-up phone visit.

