All participants who discontinue study treatment should comply with protocol-specified follow-up procedures as outlined in [Section 2](#). The only exception to this requirement is when a participant withdraws consent for all study procedures including post-treatment study follow-up or loses the ability to consent freely (ie, is imprisoned or involuntarily incarcerated for the treatment of either a psychiatric or physical illness).

If study treatment is discontinued prior to the participant's completion of the study, the reason for the discontinuation must be documented in the participant's medical records and entered on the appropriate CRF page.

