9.2.1 Time Period and Frequency for Collecting AE and SAE Information

All SAEs must be collected from the time of signing the consent, including those thought to be associated with protocol-specified procedures and within 56 days of discontinuation of dosing.

The investigator must report any SAE that occurs after these time periods and that is believed to be related to study treatment or protocol-specified procedure (eg, a follow-up skin biopsy).

- Medical occurrences that begin before the start of study treatment but after obtaining informed consent will be recorded on the appropriate section of the CRF module.
- All SAEs will be recorded and reported to Sponsor or designee within 24 hours, as indicated in [Appendix 3](#).
- The investigator will submit any updated SAE data to the Sponsor or designee within 24 hours of updated information being available.

Investigators are not obligated to actively seek AEs or SAEs in former study participants. However, if the investigator learns of any SAE, including a death, at any time after a participant has been discharged from the study, and he/she considers the event reasonably related to the study treatment or study participation, the investigator must promptly notify the Sponsor.

The method of evaluating and assessing causality of AEs and SAEs and the procedures for completing and reporting/transmitting SAE reports are provided in [Appendix 3](#).

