9.4 Safety

Planned time points for all safety assessments are listed in [Section 2](#) (Schedule of Activities).

On Day 1, the results of all assessments must be reviewed to assure that eligibility requirements are met before contacting the Central Randomization System for the participant's randomization assignment.

Participants who terminate treatment early should complete the appropriate ET Visit and the PTFUP Visits. The ET Visit should be as soon as possible after the last dose of study medication.

All assessments should be performed or administered prior to study drug administration unless otherwise indicated.

Only data for the procedures and assessments specified in this protocol should be submitted to the Sponsor on a CRF. Additional procedures and assessments may be performed as part of standard of care; however, data for these assessments should remain in the participant's medical record and should not be provided to the Sponsor, unless specifically requested by the Sponsor.

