10.3.2 Safety Analyses

The proportion (%) of participants with AEs, deaths, SAEs, AEs of special interest, and AEs leading to discontinuation and of participants with laboratory marked abnormalities will be provided by treatment group. Summaries for the SBTP will include events from the start of study treatment up to start of the OLTP for participants continuing in the OLTP or up to last dosing date +56 days for participants discontinuing during the SBTP using the as-treated analysis population. AEs of special interest are infections, malignancies, autoimmune disorders, and injection-site reactions. Summaries for the cumulative abatacept period will include safety events with onset on or after the first day of abatacept treatment in the study up to 56 days after the last abatacept treatment in the study using the cumulative abatacept population.

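### Participants who take post-study abatacept have no scheduled contact covering the 56-day safety window, and the protocol contradicts itself on whether early stoppers among them are excused from follow-up

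*Combined protocol and SAP*

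**What the plan says.** Section 5.1.3 plans "2 follow-up visits on Day 85 and Day 169 post cessation of investigational product", then releases anyone who goes on to abatacept after the study. The release from the PTFUP covers people who finish the open-label treatment period (OLTP) and people who "discontinue at any time prior to completing the OLTP AND are treated with post-study abatacept, regardless of the source, will not need to complete" it. The synopsis says the same. The Table 2-4 footnote restricts both visits to those who have finished or stopped "AND are not treated with abatacept as a post-study drug".

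Two other places send people to the PTFUP and mention no release. Section 9.4 states: "Participants who terminate treatment early should complete the appropriate ET Visit and the PTFUP Visits". Footnote a of Table 9.4.7-1 has any participant who becomes pregnant stop study treatment and enter the PTFUP.

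The safety windows make no exception either. Section 9.2.1 requires SAEs to be collected from consent "and within 56 days of discontinuation of dosing". Section 10.3.2 counts events for the single-blind treatment period (SBTP) "up to last dosing date +56 days for participants discontinuing during the SBTP using the as-treated analysis population", and for the cumulative abatacept period to 56 days after the last in-study abatacept dose. Section 9.2.5 makes exposure in pregnancy reportable for at least 70 days after study product. Section 9.2.1 also says: "Investigators are not obligated to actively seek AEs or SAEs in former study participants".

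**The concern.** For the excused group, the exemption removes the only contacts scheduled after treatment ends. Section 9.4 wants the ET visit as soon as possible after the last dose, so that visit cannot look back over the 56 days. Collection and analysis therefore both assume a window that nobody is scheduled to ask about. The same people lose both urine pregnancy tests in Table 2-4.

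Section 10.3.2 reports percentages of participants. A missed event can lower the numerator while the denominator stays the same. The SBTP summary matters most, because it compares the randomized arms. There, being excused depends on a choice made after randomization, to take the drug of one of the two arms, by participants and treating physicians who know the allocation (Section 7.3). Separately, the contradiction means that two sites could treat the same kind of early stopper differently and each be following the protocol.

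**Working it through.** No figure in the plan needs reproducing. The check compares passages and counts days.

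**1. Passages side by side**
- Early stopper who takes post-study abatacept: excused under the synopsis, Section 5.1.3 and Table 2-4; not excused under Section 9.4.
- Pregnant participant who takes post-study abatacept: excused under the same three places; sent to the PTFUP by the Table 9.4.7-1 footnote.
- Section 8.1 is not a further conflict. Its sentence, "All participants who discontinue study treatment should comply with protocol-specified follow-up procedures as outlined in" Section 2, points to the section that contains the exemption.
- The 56-day sentence in Section 9.2.1 covers SAEs only, whereas Section 10.3.2 counts all AEs. For non-serious AEs in an excused participant, there is neither a scheduled contact nor a stated 56-day collection duty.

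**2. Excused OLTP completers**
- Last dose Day 722 (Section 7.1.1, taken on its target day); final visit Day 729 ± 7 (Table 2-3); window 56 days (Section 10.3.2).
- Window ends: 722 + 56 = Day 778.
- Days with no scheduled contact: 778 − 729 = 49, and 49/56 = 87.5%.
- With the visit window: 778 − 736 = 42 to 778 − 722 = 56 days.

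**3. Excused SBTP stoppers**
- Up to 56 days, less any delay between the last dose and the ET visit.

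**4. Participants who are not excused**
- For early stoppers the PTFUP starts on the day of last treatment. The first visit, at Day 85 ± 10 (Table 2-4), falls 75 − 56 = 19 to 95 − 56 = 39 days after the window closes. Their window is covered only in retrospect, but it is covered.

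**5. Possible number of excused SBTP stoppers (rates assumed; none are in the documents)**
- Excused per arm = 150 × d × f, where d is the proportion stopping and f the proportion of stoppers taking post-study abatacept.
- d = 5%, f = 10%: 150 × 0.05 × 0.10 = 0.75.
- d = 20%, f = 50%: 150 × 0.20 × 0.50 = 15.
- At the upper end, uncovered time is 15 × 56/365.25 = 2.3 person-years. At an assumed 0.20 SAEs per person-year, about 0.46 SAE would be expected in it. The rate just after stopping could be higher than any average rate.

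**6. Split between arms (rates assumed)**
- Adalimumab share = b/(a + b), where a and b are the excused numbers on abatacept and adalimumab.
- Stopping 10% in each arm, uptake 10% against 30%: a = 1.5, b = 4.5, share 75%.
- Equal stopping and equal uptake: 50%.
- Stopping 15% against 5%, uptake 30% against 10%: a = 6.75, b = 0.75, share 10%.
- No uptake among abatacept stoppers: 100%.

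**The case against.** The strongest reply is that the duty to collect SAEs to 56 days still binds sites for excused participants. The sentence about not seeking events concerns former participants, and the one after it speaks of people discharged from the study. Applying it inside the mandatory window is an inference. If Section 9.4 governs, early stoppers attend the PTFUP and the between-arm issue disappears. The SBTP numbers are small, the safety tables are descriptive, and the primary and key secondary endpoints are untouched. Most of this stands, and it limits the point to a risk of under-capture. It does not supply a scheduled contact to carry out the duty, and it does not settle which rule governs.

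A reader might infer that the gap falls mainly on adalimumab stoppers and so flatters adalimumab. It is plausible that someone stopping adalimumab is more likely to start abatacept than someone who stopped abatacept for harm or lack of effect. The documents do not support the stronger claim:
- The rule applies equally to both arms, and no stopping or uptake rates are given. Step 6 ranges from 10% to 100%.
- Section 5.1.2.2 gives continuing adalimumab participants study abatacept at Week 24, which weakens the motive to leave for it. It sends those who decline it to the PTFUP.
- Section 10.3.2 ends the SBTP count at the start of the OLTP for those who continue, but does not end it when a stopper starts outside abatacept. Such events would count under adalimumab, which works against an under-count in that arm.

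**Conclusion.** The point holds as a conflict between passages and an uncovered window. Excused participants have no scheduled contact for about 49 of the 56 counted days if they complete the OLTP (42 to 56 with the visit window), and for up to 56 if they stop in the SBTP. These day counts rest only on stated days and windows. The number of people affected, about 1 to 15 per arm among SBTP stoppers, rests on assumed rates; the number of excused completers cannot be derived.

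Under-capture could differ by arm, but neither its size nor its direction follows from the documents. Two stronger readings fail. The window is not one that can never be observed, because the SAE duty remains. Nor should the gap be expressed as patient-years lost from a rate, because Section 10.3.2 plans percentages of participants, with no person-time denominator. The matter is worth correcting because the remedy is cheap and improves safety capture.

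**What to change.** - Reconcile the synopsis, Section 5.1.3 and Table 2-4 with Section 9.4 and the Table 9.4.7-1 footnote, so that one rule states who attends the PTFUP.
- For every participant still excused, schedule one telephone contact for AEs, SAEs and pregnancy at or after the end of the stated window. A call at or after 70 days from the last dose would cover both the 56-day safety window and the 70-day pregnancy period. The Table 2-4 footnote already allows telephone follow-up when an in-person visit is not possible.
- Record the start date of post-study abatacept.
- State in Section 10.3.2 how events after that date but within the 56 days are attributed, for example flagged and tabulated with and without them. Without such a rule, better capture would add events on outside abatacept to the adalimumab column.
- Do not end the counting window at the last contact. With percentages of participants, that could only discard events that were reported.

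The cost is one call per excused participant, one extra date field, protocol wording, and a small addition to the safety tables. Treatment rules do not change.
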